#### 3.4 Replacement of Subjects

Ineligible subjects (ie, subjects who were exposed to investigational product but post hoc were found to be ineligible) may be replaced.

Subjects enrolled in Part 1 may be replaced if they are not evaluable for DLT. Subjects will NOT be considered DLT evaluable if:

- the subject did not receive study treatment
- the subject missed 2 consecutive doses out of the 4 planned doses for reason(s) other than DLT during the DLT evaluation period
- the subject ended the study treatment before completion of DLT evaluation period for a reason other than experiencing a DLT.

Exception to this rule is:

Discontinuation of treatment due to early progression after receiving at least 3 doses of investigational product and safety follow-up data for entire DLT evaluation period are available.

All available safety data for subjects who are not DLT evaluable will still be evaluated and considered in DLRT recommendations.

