#### 6.2.1.3 Dose Limiting Toxicities (DLTs)

The DLT window (ie, DLT evaluable period) will start on Day 1 (start of the administration of the first infusion). The duration of the DLT window is 28 days from infusion Day 1.

The DLT window may also be extended to assess events starting within the window in case the DLT definition is time dependent.

See Section 3.4 for description of DLT evaluability and replacement of subjects.

All available safety data for subjects who are not DLT evaluable will still be evaluated and considered in DLRT recommendations.

A DLT will be defined as any of the events described below occurring in a subject during the DLT window unless clearly attributable to causes other than AMG 562 treatment. The CTCAE version 4.0 (see Appendix A) will be used to assess toxicities/adverse

events with the exception of CRS and tumor lysis syndrome (TLS). See Section 6.2.1.4 and Appendix K for grading criteria of CRS, neurotoxicity and TLS respectively.

- 1. Death not clearly due to the underlying disease or extraneous causes.
- 2. Any subject meeting the criteria for Hy's Law case (ie, severe drug-induced liver injury [DILI]) will be considered a DLT. A Hy's Law case is defined as: AST or ALT values of ≥ 3x ULN AND with serum total bilirubin (TBIL) level of > 2x ULN or INR > 1.5 without signs of cholestasis and with no other clear alternative reason to explain the observed liver-related laboratory abnormalities (see Section 6.4 for hepatotoxicity management and Appendix A for further explanation of Hy's law case and Management of Hepatic Function)
- 3. Non-hematologic DLTs:
  - Non-hematological adverse event grade 3 or higher, EXCEPT:
    - infection responding to antibiotic/anti-infective treatment within 48 hours
    - grade 3 fatigue or asthenia
    - grade 3 headache that improves to grade ≤ 2 within 72 hours
    - grade 3 insomnia that improves to grade  $\leq$  2 within 72 hours
    - grade 3 fever that improves to grade  $\leq$  2 within 72 hours
    - grade 3 nausea, vomiting or diarrhea responding if managed with optimal medical support and resolves within 72 hours
    - laboratory parameters of grade ≥ 3, not considered clinically relevant , and improved to grade ≤ 2 within 72 hours
- 4. Hematologic DLTs:
  - Febrile neutropenia grade 3 or higher unless responding to antibiotic/anti-infective treatment within 48 hours
  - Grade 4 neutropenia lasting more than 5 days
  - Grade 4 thrombocytopenia lasting more than 7 days

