# Table 6. Infusion Interruptions/Delays/Withholding/Permanent Discontinuations and Management of Adverse Events Including Dose Reductions

	Interruption/ Delay	Specific Management	Re-start guidance	Permanent Discontinuation					
Infusion-related	ifusion-related Reaction (continued)								
Grade 3	Immediate interruption/ delay until event has improved to grade ≤ 1	Consider supportive therapy including steroids as clinically indicated. Increase monitoring of vital signs as medically indicated until the subject is deemed medically stable.	
 
As for grade 2 infusion-related reaction, with the exception of mandatory dose modification: reduce to next lower dose
 
	If subject missed more than 2 consecutive doses If recurrent grade 3					
Recurrent Grade 3 despite reduction of infusion rate & other measures	Immediate interruption	As for grade 3 infusion-related reaction	• n/a	Immediately stop the infusion (if applicable) and permanently discontinue AMG 562 therapy					
Grade 4	Immediate interruption	As for grade 3 infusion-related reaction	n/a	Immediately stop the infusion (if applicable) and permanently discontinue AMG 562 therapy					
Cytokine Releas	se Syndrome								
For Grading, Sto	or Grading, Stopping and Re-challenge Rules please refer to Table 7.								

Footnotes defined on last page of table

Page 2 of 5

Table 6. Infusion Interruptions/Delays/Withholding/Permanent Discontinuations and Management of Adverse Events Including
Dose Reductions

	Interruption/ Delay	Specific Management	Re-start guidance	Permanent Discontinuation
Any other adv	verse events including th	hose not meeting DL	.T criteria	
≥ Grade 3	Interruption/ delay required if deemed intolerable by the subject and not responding to appropriate medical management until event has improved to grade ≤ 1	n/a	
 
Re-start possible if successfully managed and improvement to ≤ grade 1 in ≤ 14 days.
 
In case of infusion interruption, continue treatment with next scheduled infusion, do not resume prior infusion or administer delayed infusion.
 
If next infusion is delayed:         
 
up to 72 hours: follow the schedule of assessments for the cycle day on which the infusion was originally planned. The following infusion should then be administered after 7 (± 1) days             

	If subject missed more than 2 consecutive doses In case of any event at grade 4

Footnotes defined on last page of table

Page 3 of 5

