# Table 6. Infusion Interruptions/Delays/Withholding/Permanent Discontinuations and Management of Adverse Events Including Dose Reductions

Page 4 of 5

Approved

Footnotes defined on last page of table

Table 6. Infusion Interruptions/Delays/Withholding/Permanent Discontinuations and Management of Adverse Events Including
Dose Reductions

	Interruption/ Delay	Specific Management	Re-start guidance	Permanent Discontinuation
Any Non	-AMG 562 related events			
Grade 4	Interruption/ delay required if deemed intolerable by the subject and not responding to appropriate medical management until event has improved to grade ≤ 1, with exception of Grade 4 neutropenia or thrombocytopenia, follow re-start guidance as indicated.	n/a	
 
Re-start possible if successfully managed and improvement to ≤ grade 1 in ≤ 14 days.
 
In case of infusion interruption, continue treatment with next scheduled infusion, do not resume prior infusion or administer delayed infusion.
 
If next infusion is delayed:         
 
up to 72 hours: follow the schedule of assessments for the cycle day on which the infusion was originally planned. The following infusion should then be administered after 7 (± 1) days
 
> 72 hours: skip the infusion and resume schedule of assessments for the next schedule infusion
 
 
 
Hospitalization: 48 hours
 
Dose modification: resume at the same dose or reduce to next lower dose if clinically indicated
 
Additional measures: premedication and additional assessments as indicated in Section 6.2.1.4.2.4 above.
 
	If subject missed more than 2 consecutive doses In case of reappearance of same event at grade 4
Hepatoto	oxicity			
For Stopp	bing and Rechallenge Rules please	e refer to Section 6.4		

Page 5 of 5

\* Obtain brain MRI and perform cerebro spinal fluid (CSF) analysis, if there are no contraindications

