- DLT (separate guidance for CRS, IRR and Neurotoxicity) or other unmanageable toxicity unless a subject has a clear clinical benefit from treatment, the toxicity has resolved to grade ≤ 1 or baseline and after consultation with the sponsor
- in case of grade 4 non-hematologic adverse event
- grade 3 neurotoxicity needing more than 7 days after treatment interruption to resolve to grade ≤1
- Grade 4 neurotoxicity
- Grade ≥ 3 seizure
- In case of occurrence of more than one seizure of grade ≤ 2
- treatment interruption: if the subject misses at least 2 consecutive doses due to serious adverse events/adverse events
- possible DILI requiring permanent withholding as per Section 6.4
- subjects who require more than 1 dose reduction
- clinically relevant disease progression
- relapse of disease subsequent to response on protocol treatment
- occurrence or progression of a medical condition which in the opinion of the investigator should preclude further participation of the subject in the study
- administration of relevant non-permitted concomitant medications
- requirement for alternative therapy
- subject's request
- subject or investigator not compliant with the study protocol

For grading of events, refer to Section 9.2.2.1.

Females who become pregnant while on study through 120 days after receiving the last dose of study drug will not receive subsequent scheduled doses and will be followed for safety until the EOS visit.

Males with pregnant partners or whose partners become pregnant while the subject is on study through 180 days after receiving the last dose of study drug must practice sexual abstinence or use a condom while on study through 180 days after receiving the last dose of study drug.

All reasons for treatment discontinuation should be clearly and comprehensively documented in the eCRF. If a subject has not continued to present for study visits, the investigator should determine the reason and circumstances as completely and accurately as possible.

In any case of premature treatment discontinuation, the investigator should make every effort to perform all examinations scheduled for the EOT.

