# 10.1.2 Analysis Sets

The analysis of all endpoints, unless noted otherwise, will be conducted on the Safety Analysis Set defined as all subjects that are enrolled and receive at least 1 dose of AMG 562.

The analysis of DLT will be conducted on the DLT Analysis Set defined as all subjects who are DLT-evaluable (see Section 6.2.1.3). DLT-evaluable subjects are those who 1) experienced DLTs or 2) completed DLT observational period and did not experience DLTs

The PK Analysis Set will contain all subjects who have received at least 1 dose of AMG 562 and have at least 1 PK sample collected. These subjects will be evaluated for PK analysis unless the number of data points required for analysis is not enough, or significant protocol deviations have affected the data, or if key dosing or sampling information is missing.

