# 10.4 Planned Analyses

### 10.4.1 Interim Analyses

In the dose escalation part, safety data will be reviewed on an ongoing basis. Based on accumulating toxicity information, BLRM will be used to make dosing recommendations. In dose level review team meetings (DLRMs), Amgen, in consultation with the site investigators, will review the BLRM recommended dose level and will review all available cumulative data by cohort prior to making dose escalation decisions. As a sensitivity analysis, a one-parameter Continual Reassessment Method model may be used to estimate the dose-toxicity relationship to help making dose escalation decisions. Adverse events and DLTs observed in all subjects will be evaluated continually and fully integrated into all DLRMs and considered in all enrollment and dosing decisions.

The clinical activity of AMG 562 in the dose expansion part will be examined using a Bayesian predictive probability design. If the posterior probability is more than 85% that the ORR is 40% or less, then this is considered insufficient anti-lymphoma activity. If the ORR is too low, enrollment may be terminated early due to insufficient anti-lymphoma activity. The guidelines for futility due to insufficient efficacy assuming a prior beta distribution (0.8, 1.2) are presented in Table 15. The operating characteristics in Table 16 provide the probability of stopping the trial early for given hypothetical true ORR rates whereas the stopping criteria in Table 15 are based on situations where the empirical evidence would result in a posterior probability of  $\geq$ 85% that the true ORR rate is  $\leq$  40%.

The DLRT will be convened in the dose expansion part of the study to review efficacy data (with recruitment ongoing) after the first 15 subjects are enrolled and have had the opportunity to receive at least five weeks of treatment (with recruitment ongoing).

Number of Treated Subjects	Efficacy Futility Guideline					
15	4 or fewer responders					
20	5 or fewer responders					
25	7 or fewer responders					
30	9 or fewer responders					
35	11 or fewer responders					
40	12 or fewer responders					
45	14 or fewer responders					
50	16 or fewer responders					
55	Trial will stop					

 Table 15. Guideline for Insufficient Efficacy

Table 16.	Operating	Characteristics for futi	ility With Batch Size of 5 Subject	S
	oporading			

True ORR Rate	Probability of Stopping Early for Futility	Average Sample Size
0.25	95%	21
0.30	81%	27
0.35	59%	36
0.40	36%	43
0.45	18%	49

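### The infection and febrile neutropenia exceptions to the DLT definition have no grade ceiling, so a responding grade 4 event usually ends treatment yet stays out of the DLT count unless another criterion applies

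*Protocol*

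**What the plan says.** Protocol 6.2.1.3 starts from non-hematologic events of grade 3 or higher and lists seven exceptions. Five (fatigue or asthenia, headache, insomnia, fever, and nausea, vomiting or diarrhea) are limited to grade 3. The other two are not. One covers laboratory values of grade 3 or above, but only if they are not clinically relevant and improve to grade 2 or below within 72 hours. The other is "infection responding to antibiotic/anti-infective treatment within 48 hours". Among the hematologic DLTs the entry is "Febrile neutropenia grade 3 or higher unless responding to antibiotic/anti-infective treatment within 48 hours". SAP section 5 defines a DLT by reference to 6.2.1.3 and adds no cap.

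Discontinuation follows a different rule:

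- Table 6, in its row for other adverse events, requires permanent discontinuation "In case of any event at grade 4".
- Table 6, in its row for events not related to AMG 562, allows restart and requires discontinuation only "In case of reappearance of same event at grade 4".
- Section 6.2.1.4.4 lists permanent discontinuation "in case of grade 4 non-hematologic adverse event", with no relatedness limit.

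On evaluability, section 3.4 excludes a subject if "the subject ended the study treatment before completion of DLT evaluation period for a reason other than experiencing a DLT", and allows replacement in Part 1. Section 10.1.2 and SAP 6.4 use looser wording, under which a subject is also evaluable who "completed DLT observational period and did not experience DLTs".

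On review, section 10.4.1 says "Adverse events and DLTs observed in all subjects will be evaluated continually and fully integrated into all DLRMs". Section 10.4.2 adds that toxicities of grade 3 or higher that are not DLTs are reviewed and may be considered.

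**The concern.** The plan gives two answers on how serious the same event is. A grade 4 infection not judged unrelated to AMG 562 is serious enough to stop the drug for good, but if it responds within 48 hours it is not dose-limiting. DLT incidence is part of the primary endpoint. It is also the input to the BLRM and to the Part 2 stopping boundary, so an event left out of it cannot move either.

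Such events are foreseeable. Neutropenia and decreased immunoglobulins are both listed in Table 4 as important potential risks, with infection prophylaxis and treatment named in the monitoring column. Section 2.2.4 reports infections and neutropenia, including febrile neutropenia, among the commonest reactions to blinatumomab, another BiTE construct that targets CD19.

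Some fixed rules in section 3.1 also depend on the DLT label. One DLT limits later escalation to 2-fold and brings in the BLRM recommendation. Two at a dose level end enrollment to that cohort.

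**Working it through.** **Step 1: is there another route into the count?**

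- *Death* (6.2.1.3, item 1) covers fatal cases not clearly due to disease or extraneous causes, so only non-fatal events are at issue.
- *Other DLT criteria* may catch the same episode, for example grade 4 neutropenia lasting more than 5 days or a separate non-hematologic event of grade 3 or higher.
- *DLRT reclassification* (6.2.1.3, closing text) applies only to events outside the window that already meet the DLT definition.
- *SAP 9.6.1* links its possible sensitivity analysis to DLTs outside the time interval, so an excused in-window event would not trigger it.

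An event caught by none of these is not counted.

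**Step 2: what happens to the subject?** If the event ends treatment inside the window, 3.4 drops the subject from the evaluable set. The wording of 10.1.2 and SAP 6.4 could instead keep the subject as a non-DLT. For one such event in Part 1:

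| Cohort | Event counted | Subject dropped | Replaced by a subject without a DLT, or kept as non-DLT |
|---|---|---|---|
| 3 subjects | 1/3 | 0/2 | 0/3 |
| 4 subjects | 1/4 | 0/3 | 0/4 |

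**Step 3: reproduce the plan's Part 2 figures.** Inputs are the Table 17 boundaries (6, 8, 10, 12, 14, 16, 18, 20, 21 DLTs at n = 10, 15, ..., 50), with an end at n = 55. The boundaries follow from the stated rule: with a beta (0.66, 1.33) prior, stop if P(rate > 0.33 | data) > 0.90. An exact binomial recursion in batches of 5 gives stopping probabilities of 1.0, 4.2, 13.0, 22.6, 31.0, 56.0 and 79.0% at true rates 0.20, 0.25, 0.30, 0.33, 0.35, 0.40 and 0.45. Table 18 prints 1, 4, 13, 22, 31, 56 and 79%. The average n is 37.5 at 0.40 and 29.1 at 0.45 (printed 37 and 29).

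**Step 4: illustration.** Let p be the DLT rate under a definition that counts these events. Let x be the share of subjects whose only qualifying event is an excused grade 4 infection or febrile neutropenia. The rate the boundary sees is

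- subject dropped: p' = (p − x)/(1 − x)
- subject kept as non-DLT: p' = p − x

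For p = 0.40 and x = 0.01, these are 0.39/0.99 = 0.394 and 0.39. The documents give no value for x; 0.01, 0.02 and 0.05 are assumptions.

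| p | x | Stop, dropped | Average n | Stop, kept | Average n |
|---|---|---|---|---|---|
| 0.40 | 0 | 56.0% | 37.5 | 56.0% | 37.5 |
| 0.40 | 0.01 | 52.9% | 38.5 | 50.8% | 39.2 |
| 0.40 | 0.02 | 49.6% | 39.5 | 45.6% | 40.8 |
| 0.40 | 0.05 | 39.8% | 42.6 | 31.0% | 45.2 |
| 0.45 | 0 | 79.0% | 29.1 | 79.0% | 29.1 |
| 0.45 | 0.01 | 76.9% | 30.0 | 75.0% | 30.8 |
| 0.45 | 0.05 | 66.5% | 33.9 | 56.0% | 37.5 |

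The average n counts DLT-evaluable subjects. Dropping the subject moves the stopping probability less than keeping the subject as a non-DLT. The loss therefore comes from the uncounted event; leaving the denominator partly offsets it.

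**The case against.** The open form may well be intended. The febrile neutropenia entry names grade 3 or higher and then excuses responders, so grade 4 was in view when it was written. The Amendment 1 summary records that the headache, insomnia and fever exceptions were tightened and mentions no change to infection or febrile neutropenia. A reader might infer a drafting slip from the five exceptions that are capped at grade 3, but the documents do not support that.

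A reader might also infer that the DLT rate is simply biased. That goes too far. The 20–33% target interval and the 33% stopping threshold refer to DLTs as the protocol defines them. Against that definition, a subject kept as a non-DLT produces no bias. The stopping probabilities above show what a broader definition would change, not an arithmetic error in Table 17 or 18.

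Nor do the documents support reading this as an event that escapes safety oversight. Sections 3.4, 10.4.1 and 10.4.2 put it before the DLRT. In Part 1, a non-hematologic event of grade 2 or higher, or one of the listed hematologic events of grade 3 or higher, triggers the switch from single-subject to multiple-subject cohorts. Two or more patients with adverse events of grade 2 or higher cap escalation at 2-fold.

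All of this stands and limits the point. It does not remove the internal conflict: review is discretionary, and neither the model input nor the boundary count changes.

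**Conclusion.** The point holds in a limited form. As written, a non-fatal in-window grade 4 infection or febrile neutropenia that responds within 48 hours is not a DLT unless another criterion applies. Unless judged unrelated, it requires permanent discontinuation, under Table 6 for both events and under 6.2.1.4.4 for infection. If it is judged unrelated, the Table 6 row for unrelated events allows restart, although the 6.2.1.4.4 bullet carries no such limit. Whether the subject is dropped or kept, the event is missing from the BLRM and Table 17 counts.

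The understatement exists only relative to a definition that counts life-threatening infection. Its size is unknown and probably small. At 1 percentage point of a 40% rate, stopping falls by 3 to 5 percentage points and the average n rises by about 1 to 2 subjects. The larger shifts rest on the assumed 5 points, which nothing in the documents supports as a likely value. With the study discontinued, the Part 2 boundary illustrates the design and can no longer affect conduct. The reported DLT incidence is what can still be clarified.

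**What to change.** In 6.2.1.3, put grade 3 in front of the infection exception, so that only a grade 3 infection meeting the existing 48-hour response condition is excused. No further improvement requirement is needed. For febrile neutropenia, count grade 4 as a DLT in every case, and grade 3 only when it has not responded to anti-infective treatment within 48 hours.

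Because the study ended early, the change that can still act is in SAP 9.6.1: one sensitivity DLT incidence table. It should count as DLTs all in-window grade 4 infections and grade 4 febrile neutropenia not clearly due to another cause, and keep those subjects in the denominator. No extra model fit is needed, since SAP section 10 already drops the summary of toxicity-interval and DLT probabilities.

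This is a cheap improvement: a few words in two bullets and one table. The cases can be found in the adverse event listing planned in SAP 9.6.2. That section omits its summary tables when two or fewer subjects have the event, so rare cases might otherwise appear only in the listing. The downside is a possibly slightly higher reported DLT rate. Responding grade 3 infections stay excepted, as now.

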#### 6.2.1.4.2.2 Infusion Interruptions due to Adverse Events

Events occurring during the infusion and requiring treatment interruption will be managed by immediate infusion interruption. The site should record any unscheduled interruption of an infusion on the eCRF, and provide the start and stop date/time of the infusion.

Events requiring infusion interruption or permanent discontinuation are listed in Table 6.

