#### 6.2.1.4.3 Specific Guidance for Neurotoxicity

**Neurotoxicity** is a broad concept, including any adverse effect on the structure or function of the central and/or peripheral nervous system by a biological, chemical or physical agent. In this definition, neurotoxic effects may be permanent or reversible and result from direct or indirect actions on the nervous system (Erinoff, 'Interagency Committee on Neurotoxicology', 1995).

In case of grade 3 or grade 4 neurotoxicity events, perform investigations per local practice including neurological exam, cerebral MRI and CSF analysis after interruption of infusion.

Dexamethasone IV or PO should be administered at a dose of  $3 \times 8 \text{ mg}$  /d over 3 days with step-wise dose reduction over up to 4 days. For seizures  $\geq$  grade 2 administer corticosteroids and antiseizure medication per local practice.

Re-start of IP is possible within 2 weeks but not earlier than 3 days after infusion was stopped and if successfully managed with improvement to  $\leq$  grade 1 in  $\leq$  7 days. Subjects will remain hospitalized for 72 hours following re-start of IP. Following grade 2 seizure, do not re-initiate AMG 562 until 7 days after the last seizure and after therapeutic levels of antiseizure medication are likely to have been achieved.

#### 6.2.1.4.4 Permanent Discontinuation of AMG 562

AMG 562 treatment will be permanently discontinued in the event of:

- infusion-related reaction grade 4 (the infusion has to be stopped immediately, if applicable)
- recurrent grade 3 infusion-related reaction despite reduction of infusion rate & other symptomatic measures
- grade 4 CRS
- grade 2 or 3 CRS meeting any of the criteria listed below:
  - grade 2 or 3 CRS that does not improve to grade  $\leq$  1 within 7 days
  - grade 3 CRS that does not improve to grade  $\leq$  2 within 5 days
  - if a subject experiences 2 separate grade 2 or grade 3 CRS events regardless of dose
  - grade 3 CRS at the initial lower dose for treatment initiation (for cohorts with step-up dosing only)
- Occurrence of acute kidney injury considered related to AMG 562 by the investigator and meeting one or more of the following criteria:
  - Creatinine > 3x baseline or > 4.0 mg/dL and not recovered to CTCAE grade 1 or ≤ 0.3 mg/dL within 21 days
  - Hemodialysis required

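### Table 6 and Section 6.2.1.4.4 disagree on whether a short grade 4 neutropenia or thrombocytopenia that is not a DLT ends treatment, and under Section 3.4 the answer decides DLT evaluability

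*Protocol*

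**What the plan says.** **DLT definition.** Protocol 6.2.1.3 lists "Grade 4 neutropenia lasting more than 5 days" among the hematologic DLTs, and grade 4 thrombocytopenia only beyond 7 days. Shorter episodes do not meet these criteria. The window is 28 days.

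**Discontinuation, Table 6.** The row for other adverse events of grade 3 or higher expressly takes in events that fall short of a DLT. Its permanent-discontinuation cell includes "In case of any event at grade 4", with no hematologic exception. Section 6.2.1.4.2.2 gives the table its authority: "Events requiring infusion interruption or permanent discontinuation are listed in Table 6".

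**Discontinuation, Section 6.2.1.4.4.** This list opens "AMG 562 treatment will be permanently discontinued in the event of" and, for grade 4 events in general, reads "in case of grade 4 non-hematologic adverse event".

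**Events judged unrelated.** A separate Table 6 row covers grade 4 events not related to AMG 562. Its interruption cell carries the words "with exception of Grade 4 neutropenia or thrombocytopenia, follow re-start guidance as indicated".

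**Evaluability.** Section 3.4 makes a subject not DLT-evaluable if "the subject ended the study treatment before completion of DLT evaluation period for a reason other than experiencing a DLT". Its one exception is early progression after at least 3 doses with safety data for the whole window. Sections 10.1.2 and SAP 6.4 point to 6.2.1.3, which points to 3.4, but they also restate the definition: "DLT-evaluable subjects are those who 1) experienced DLTs or 2) completed DLT observational period and did not experience DLTs".

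**The concern.** A site facing a three-day grade 4 neutropenia that may be related to AMG 562 finds two operative discontinuation lists. One requires permanent discontinuation and the other does not. No text says which prevails.

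The first stake is the patient: someone with relapsed or refractory lymphoma may lose treatment at one site for a short cytopenia that another site doses through. The event is foreseeable. Protocol 2.3 names neutropenia as an important potential risk and reports it among the most common reactions to blinatumomab.

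The second stake is the DLT denominator. DLT incidence is part of the primary endpoint, feeds the BLRM and is the count in Table 17. A subject stopped inside the window for a short cytopenia leaves the denominator. The same subject kept on treatment stays in it as no DLT. Only non-DLT subjects can be lost this way, so the observed DLT rate can only move up.

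**Working it through.** **1. The rules side by side, for a three-day grade 4 neutropenia starting on day 10, after the day 1 and day 8 doses**

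| Rule followed | Treatment | DLT status |
|---|---|---|
| 6.2.1.4.4 | may continue | evaluable, no DLT |
| Table 6, other adverse events | permanently stopped | not evaluable under 3.4 |

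Under Table 6 the subject also misses days 15 and 22. These are two consecutive doses missed for a non-DLT reason, which is a second ground for non-evaluability in 3.4.

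**2. Table 17 reproduced**

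Inputs from 10.4.1: prior Beta(0.66, 1.33); stop if P(rate > 0.33) > 0.90. The boundary at n is the smallest x for which 1 − F(0.33; 0.66 + x, 1.33 + n − x) > 0.90, where F is the beta distribution function. For n = 10, 15, …, 50 this gives 6, 8, 10, 12, 14, 16, 18, 20, 21, and all nine match. Exact crossing probabilities at true rates 0.25, 0.30, 0.33, 0.35 and 0.40 are 4.2, 13.0, 22.6, 31.0 and 56.0%. Table 18 gives 4, 13, 22, 31 and 56%.

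**3. Part 2 if these subjects are removed**

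Let g be the share of treated subjects with a non-DLT grade 4 hematologic event who are taken out. The documents give no value, so 5, 10 and 20% are assumed. The DLT rate among those left is p/(1 − g). With p = 0.30:

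- g = 5%: 0.30/0.95 = 0.316
- g = 10%: 0.30/0.90 = 0.333
- g = 20%: 0.30/0.80 = 0.375

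With 55 treated, the number evaluable is Binomial(55, 1 − g), and Table 17 is applied at each look reached:

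| True DLT rate | g = 0 | 5% | 10% | 20% |
|---|---|---|---|---|
| 0.25 | 4% | 6% | 8% | 15% |
| 0.30 | 13% | 18% | 23% | 37% |

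The look at 50 evaluable is reached in 94, 52 and 2% of trials for g = 5, 10 and 20%. These are upper figures for each assumed share, because every such subject is removed. If half were removed, the 0.30 row would be about 15, 18 and 23%.

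**4. Part 1**

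Appendix J fixes the prior through four statements: a median DLT probability of 0.40, and P(rate ≤ 0.05) = 0.05, at the reference dose; a median of 0.01, and P(rate ≤ 0.40) = 0.90, at the lowest dose. On the relative log-dose scale these suffice without the redacted doses, if zero correlation is assumed. The intercept is then normal with mean logit(0.40) and SD 1.54. The slope over the range is lognormal with median 4.19 and log-SD 1.61. A dose is allowed if P(rate > 0.33) is below 0.40. Each row compares 1 DLT in 4 with 1 in 3, the latter after removing one non-DLT subject:

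| Cohort and history | 1 in 4 | 1 in 3 | Decision differs? |
|---|---|---|---|
| Reference dose; two DLT-free single subjects below | 37% | 49% | yes |
| 10% of the log range lower; same history | 27% | 37% | no |
| Reference dose; same history plus 1 in 4 at mid-range | 46% | 57% | no, both barred |
| Reference dose; DLT in the second single subject | 62% | 73% | no, both barred |
| 10% of the log range lower; two DLT-free single subjects plus 1 in 4 at 30% below reference | 38% | 48% | yes |

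If the removed subject is replaced by one without a DLT, 1 in 3 becomes 1 in 4 again and the difference disappears.

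**The case against.** **The lists may not conflict.** Section 6.2.1.4.4 does not say that it is exhaustive, so a site that stops under Table 6 breaches neither text. A stricter rule for possibly related events is also defensible in a first-in-human study. It stands that the stricter rule may be intended. But if every grade 4 event were meant to end treatment, the word non-hematologic in 6.2.1.4.4 would have no function, so one of the two texts needs correcting.

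**Part of the decisive row cannot be read.** The re-start cell of the other-adverse-events row is cut in the available text. A reader might infer that the neutropenia and thrombocytopenia exception exists only for unrelated events. That cannot be verified, and in the unrelated row the exception sits in the interruption cell, not the discontinuation cell. The point rests only on the discontinuation cell, which is legible.

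**A third outcome.** From the restated definition in 10.1.2 and SAP 6.4, a reader might infer that a stopped subject who is merely observed to day 28 still counts as no DLT. The documents largely close this reading: both sections lead through 6.2.1.3 to 3.4, which sets a treatment condition. The restatement is loose but does not establish a separate rule.

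**Effect on dosing.** A reader might infer that the conflict changes Part 1 dose decisions. The documents do not show this. Section 3.4 permits replacement, and 6.2.1.4.2.3 calls for it after missed doses. The Amendment 4 summary records a DLT in an early cohort, so a DLT-free history is not the relevant one. The dose review team also sees safety data from non-evaluable subjects.

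**Early termination.** The study was discontinued, and SAP Section 10 drops the DLT and interval probabilities. Amending Table 6 now would protect few if any further patients. SAP 9.6.1 still reports DLT incidence, so the Part 1 denominator still has to be settled.

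**Conclusion.** The conflict is real and should be corrected. For a possibly related grade 4 neutropenia of 5 days or less, or thrombocytopenia of 7 days or less, Table 6 requires permanent discontinuation and 6.2.1.4.4 does not. Inside the window, 3.4 then makes that choice decide whether the subject counts. The effect on treatment needs no modelling.

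The statistical effect is one-directional but limited. In Part 1 it depends on dose, history and replacement, and no change in an actual decision is shown. In Part 2 as designed, at a true DLT rate of 0.30, the stop probability rises from 13% to at most about 18, 23 or 37%. Those figures assume that 5, 10 or 20% of subjects have such an event, that all are removed, that none of them also has a DLT, and that 55 are treated without replacement.

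**What to change.** 1. In Table 6, row for other adverse events, limit the discontinuation cell to non-hematologic events at grade 4, matching 6.2.1.4.4. If the stricter rule is intended, change 6.2.1.4.4 instead.
2. In 3.4, extend the existing progression exception to stops for a non-DLT adverse event: evaluable as no DLT if at least 3 doses were given and safety data cover the whole window, otherwise not evaluable. Say whether the stricter missed-dose note for single-subject cohorts in 6.2.1.4.2.3 still applies.
3. In 10.1.2 and SAP 6.4, replace the restated definition with a direct reference to 3.4. In SAP 9.6.1, list subjects excluded from the DLT set with the reason.

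The cost is one table cell, one or two sentences and two cross-references, plus a short listing. No new data are needed: neutrophil and platelet counts, dosing and discontinuation reasons are already collected, so items 2 and 3 can be applied to the existing Part 1 data. The downside is small: a few subjects with a full window but an incomplete fourth dose would count as no DLT.
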